### **3.3.11 Data analyses**

*1) Primary Outcomes:* The impact of the intervention will be evaluated based on the change in stigma score for each study group (follow-up stigma score minus baseline stigma score). Change in HIV stigma from baseline to follow-up periods will be calculated and compared between the intervention and control arms using multi-level linear mixed models.

*2) Secondary Outcomes:* We will use logistic regression to compare HIV testing uptake (i.e., ordered HIV self-test from website) during the 3-month period between individuals in the intervention arm vs. the control arm. We will also use logistic regression to compare differences in self-reported HIV test uptake and linkage to HIV care (for those with a positive HIV rapid test result).

We will also assess feasibility and acceptability of the intervention.

## **4 Ethical Considerations**

### ***4.1 Risk Analysis***

#### **4.1.1 Risk to the participants**

The primary risks to participants are psychological discomfort from answering sensitive questions and loss of confidentiality. To address these issues, participants will be informed that they can skip any question they do not feel comfortable answering. Participants contact information will also be stored in a secure, password-protected database that is only accessible by authorized research staff. In addition, boxes containing HIV self-test kits will be plain boxes that do not indicate the contents of the box. Participants may choose to have the boxes mailed to a secure public mailbox where they can pick-up the test instead of having it mailed to their home address.

#### **4.1.2 Benefits of the study**

Participants will have access to order HIV self-tests, which they may not have previously been aware of. Participants may also experience lower levels of stigma due to their participation in the study. For individuals who test HIV positive, they will have the benefit of research staff to help link them to follow-up care. Through their participation, participants may also contribute to the development of an HIV stigma reduction and self-testing intervention that can be distributed more broadly in Kazakhstan to help the larger population of AYA.

#### **4.1.3 Alternatives to Participation**

Participants may choose not to participate in the study or drop out of the study at any time and request to have their data removed from the study database.

#### **4.1.4 Compensation**

Participants will be compensated for their time and effort based on compensation rates used in similar studies. Participants will receive approximately \$10 USD for completion of each of the surveys and for the interviews. In addition, participants completing all follow-up surveys will be entered in a raffle to win small prizes.

#### **4.2 Confidentiality**

To minimize risk, we will employ staff members who have been trained in human subjects protections and HIV pre- and post-test counseling. Study staff have had many years of experience conducting HIV research. The study consent form will inform participants of confidentiality procedures. Participants will be told that they may decline to answer questions or may withdraw from the study at any time.

For the baseline and follow-up assessments, all data will be directly entered online into Columbia University School of Social Work's Qualtrics system. Surveys will be tested to ensure accuracy, completeness, and internal consistency. Upon completion of the study, a dataset that contains only non-identifiable data will be downloaded for analysis in statistical software programs. During collection of the data, all data will be transmitted securely using SSL (TLS) 128-bit encryption across the internet. SSL provides users with the assurance of access to a valid site and prevents data interception or tampering with information. Data will be located on a secured server at Columbia University. Access to the data will be password protected.

We will use standardized methods for HIV testing photo verification that have been used in other studies. WhatsApp has secure end-to-end encryption using a Signal protocol. This ensures that only authorized research staff will be able to see the photo and any chat messages between participants and research staff. End-to-end encryption prevents third parties and WhatsApp from having access to messages or calls. Even if encryption keys from a user's device are ever physically compromised, they cannot be used to decrypt previously transmitted messages. In addition, the

photos submitted will not be labeled with any identifying information. They will simply be a photo of a test result.

No presentation or publication of the study results will refer to participants individually. Results will be reported in aggregate form. Exceptions to confidentiality for participants are those required by law and include reports of child or elder abuse and the threat of suicide or homicide. Although we are not asking questions about child or elder abuse and do not expect any such instances to be reported, participants will be informed of these exceptions in the informed consent process.

#### ***4.3 Data and Safety Monitoring Procedures***

The study processes will be monitored on a weekly basis. The study team will review all the collected data, check the study procedures, and discuss study problems and reported adverse events (if any) weekly. In addition, the recruitment and randomization procedures for both arms will be double-checked.

#### ***4.4 Compliance***

Drs. [name] and [name] will lead the implementation of the study and overall study coordination. Drs. [name] and [name] will be responsible for overseeing all study procedures and for research and fiscal administration. The research team will communicate weekly to discuss the design, data analysis, subject safety, and any administrative issues. All research results will be shared with Co-PIs, key personnel, and consultants. The Co-PIs will work together to discuss any challenges in the research project.

#### ***4.5 Participant Withdrawal***

Participants will be informed that they may withdraw from the study at any time without any consequences.

#### ***4.6 Institutional review board***

The protocol for the proposed research will be reviewed and monitored by the Columbia University IRB (FWA00003831) and the Al-Farabi Kazakh National University IRB (FWA00031261).

#### ***4.7 Informed consent***

All participants in this study will provide informed consent prior to participation in any research procedures. Participants will be well informed about the purpose of this study, potential risks of the study, and the research procedures conducted during the study. Participants will complete informed consent online through Columbia University School of Social Work's Qualtrics platform. For adolescents under 18, we are requesting a waiver of parental permission because the study is minimal risk and adolescents 16 and older are allowed to obtain an HIV test without parental permission in Kazakhstan.

### **5 Future Use**

#### ***5.1 Contact for future research studies***

During the informed consent process, participants will be asked if they would like to be contacted for future research studies. Participants who give permission to be contacted will have their contact information retained and may be contacted by the research team if they conduct future research studies among this population.

#### ***5.2 Contact for future research studies***

Participant research data will be retained for future data analysis by the research team. Per NIH guidelines on data sharing, the research team will share data with any other Columbia University researcher who has obtained IRB approval to access the data and has proposed a specific research question for data analysis. The research team will also share data with any outside researcher who has obtained IRB approval to access the data, has a signed Data Use Agreement between Columbia University and their

home institution, and has proposed a specific research question for data analysis.

1. INTRODUCTION

The JasSpark study used a community-based participatory approach that engaged local adolescents and young adults (AYA) in Kazakhstan to develop a crowdsourced digital HIV stigma reduction and self-testing intervention to reduce HIV stigma and increase HIV testing among AYA in Kazakhstan. We then pilot tested this crowdsourced HIV stigma reduction and self-testing intervention in a preliminary efficacy trial to assess feasibility and acceptability and obtain preliminary estimates of its effects on decreasing HIV stigma (primary outcome) and increasing HIV testing (secondary outcome) among AYA who received the intervention compared to individuals who did not.

This document outlines the statistical analysis plan that will be followed to assess outcomes.

Primary Outcome: To evaluate the change in HIV stigma score (follow-up stigma score minus baseline stigma score) from baseline to the three-month follow-up between the intervention and control arms.

Secondary Outcome 1: To compare HIV self-testing uptake by the three-month follow-up period between AYA in the intervention and control arms.

2. HYPOTHESES

The **primary** null (H_0) and alternative (H_A) statistical hypotheses are:

H_{P0} : HIV stigma throughout the three-month follow-up period will not differ between the intervention and control arms.

H_{PA} : HIV stigma at three-months follow-up will significantly decrease in the intervention arm compared to the control arm.

The **first secondary** null (H_0) and alternative (H_A) statistical hypotheses are:

H_{S10} : HIV self-testing uptake by three-months follow-up will not differ between the intervention and control arms.

H_{S1A} : HIV self-testing uptake by the three-month follow-up will be higher in the intervention arm compared to the control arm.

The **second secondary** null (H_0) and alternative (H_A) statistical hypotheses are:

H_{S20} : Changes in HIV stigma from baseline to the three-month follow-up period will not be moderated by sex at birth.

H_{S2A} : Changes in HIV stigma from baseline to the three-month follow-up period will be moderated by sex at birth.

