### **3.3.5 Recruitment Procedure**

AYA will be recruited through flyers, email, and social media accounts operated by youth organizations in Kazakhstan. Interested participants will complete an online eligibility screening survey. If eligible, participants will progress to the informed

consent screen, where they will read information about the study and be asked to provide informed consent. Contact information for study staff will be provided in case participants have any questions about the study. Because the study is minimal risk and Kazakh law allows adolescents ages 16 and older to order HIV-test kits without parental permission, we are requesting a waiver of parental permission to participate in the pilot RCT. Once individuals provide informed consent, they will complete a baseline survey and be randomized 1:1 to receive the digital intervention content or the standard AIDS Center content. In both arms, after the content is presented, there will be a link provided to order an HIV self-test kit from Columbia University's Global Health Research Center of Central Asia's (GHRCCA's) website, where AYA will input the address they would like to receive the test at into the order form. (This address may be a secure public mail box (similar to Amazon locker) and does not need to be their home address.)

Participants will be asked for their email addresses and/or phone numbers as contact information for follow-up surveys. Participants in the intervention arm will be sent intervention content once a week for one month via Qualtrics link. All participants will be sent follow-up surveys through Qualtrics at the one month and three month periods after baseline completion. Participants who do not complete the follow-up survey within a week will be sent an email and/or text message reminding them to complete the survey. All individuals who enroll in the study will receive ~\$10 USD for each assessment as a phone card or gift card. Those who complete all surveys will be given an opportunity to win a small prize through a raffle.

Participants ordering an HIV test will receive a message via WhatsApp using standardized methods to submit a photo of their HIV test result. Participants can submit photos of HIV self-test results to confirm HIV test uptake at any time after enrollment.

Any persons with newly identified HIV infection will be referred for treatment at the Almaty AIDS Center in accordance with standard clinical procedures.

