3.2.2. HIV Self-Testing Uptake

AYA who clicked on the survey link could fill out an online form to order an HIV self-test kit. The kit could be mailed to their home address or another location of their choosing, or ordered for pick-up at a local non-governmental organization. Participants sent pictures of their self-test results via WhatsApp to an RA. Participants who screened positive for HIV would be referred to a youth clinic and the Almaty City AIDS Center for confirmatory testing. However, none of our participants screened positive for HIV.

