4.2. Dependent Variables

The dependent variables in this analysis are:

1. Self-Reported HIV Stigma – Assessed by a 17-item HIV stigma scale that was originally developed for community members not living with HIV in South Africa and Zambia.¹ The scale was reviewed by our Community Collaborative Research Board (CCRB), and we conducted cognitive interviews with 10 Russian-speaking AYA and nine Kazakh-speaking AYA. AYA and our CCRB provided feedback on the cultural and age-appropriateness of the items, and gave recommendations on item modification. Item response options were on a five-point Likert scale (1 – strongly disagree to 5 – strongly agree). The total score across the 17 items was calculated, with a maximum total score of 85. Scale reliability was high in our sample ($\alpha=.871$).

2. HIV Self-Testing Uptake – Number of AYA in each arm who ordered an HIV self-test kit in the follow-up period after the pre-intervention assessment.

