4.5. Statistical Analysis Methods

Descriptive statistics of key independent variables and covariates will be summarized within each arm using frequencies or means (standard deviations) as appropriate. Overall participation rates will be reported in each arm based on the proportion of baseline participants who completed the three-month follow-up assessment.

To test **hypothesis 1 (H1)**, we will conduct multilevel linear mixed models to assess for differences in changes in the overall HIV stigma score between study arms. As a secondary analysis, we will also assess changes in each of the stigma subscale scores (perceived stigma in the community, fear and judgement, perceived stigma in healthcare settings, and HIV testing stigma). To account for multiple comparisons arising from analyses of subscales, the false discovery rate (FDR) was controlled using Benjamini-Hochberg procedures in a tiered approach.²

To test **hypothesis 2 (H2)**, we will use a generalized linear model using a binomial distribution to examine whether the intervention was associated with increased HIV self-testing uptake in the follow-up period. The model was adjusted for history of HIV testing (pre-intervention testing and testing prior to the study), whether the participant had submitted content to the JasSpark contest, and if the participant had a main intimate partner (e.g., girlfriend/boyfriend, spouse).

To test **hypothesis 3 (H3)**, we examined potential moderation effects of sex at birth on stigma changes. Fixed effects corresponding to the two-way interactions involving sex, time, and/or arm, as well as the three-way interaction of sex, time, and arm, were added to the models from

H1. To account for multiple comparisons arising from analyses of moderating effects, the false discovery rate (FDR) was controlled using Benjamini-Hochberg procedures in a tiered approach.²

The model testing H3 is summarized as Equation H3:

HIV stigma score = Intercept + B₁(Arm) + B₂(Categorical variable corresponding to timepoint of stigma assessment; two degrees of freedom) + B₃ (Arm * Timepoint of stigma assessment; two degrees of freedom) + B₄(Baseline stigma level) + B₅(Respondent Sexual orientation) + B₆(Respondent Age) + B₇ (Respondent Sex) + B₈ (Respondent Submitted entry to JasSpark contest) + B₉ (Respondent HIV testing prior to study) + B₁₀ (Respondent HIV testing baseline) + Error
+ Random effects for the clustering within participant across timepoints and by dyad.

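### Self-testing uptake is measured only as ordering a kit, and the protocol's companion comparison of self-reported testing is missing from the SAP without a reason

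*SAP*

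**What the plan says.** - **Aim and hypothesis.** The SAP introduction gives increasing HIV testing as the secondary aim. SAP 2 turns this into the alternative hypothesis that "HIV self-testing uptake by the three-month follow-up will be higher in the intervention arm compared to the control arm".
- **Outcome.** SAP 4.2 defines uptake as "Number of AYA in each arm who ordered an HIV self-test kit in the follow-up period after the pre-intervention assessment". It contains no element of receipt, use or result.
- **Model.** SAP 4.5 has one uptake analysis: "we will use a generalized linear model using a binomial distribution to examine whether the intervention was associated with increased HIV self-testing uptake".
- **Protocol definition.** Protocol 3.3.11 lists first a comparison of "HIV testing uptake (i.e., ordered HIV self-test from website") over three months, so the order-based definition starts there.
- **Protocol companion outcome.** The same paragraph continues: "We will also use logistic regression to compare differences in self-reported HIV test uptake and linkage to HIV care", the latter for those with a positive rapid test.
- **Photos.** Protocol 3.3.5 says "Participants can submit photos of HIV self-test results to confirm HIV test uptake at any time after enrollment". SAP 3.2.2, under the heading on self-testing uptake, reports that "Participants sent pictures of their self-test results via WhatsApp to an RA". Neither analysis section names a photo-confirmed endpoint.

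**The concern.** Ordering comes before testing. Under SAP 3.2.2 a kit was mailed or collected from a local organisation, so receipt and use both follow the order. Protocol 2.1 says that many young people avoid testing because they fear a positive result, and that barrier can still act once a kit is in hand. The protocol had a second measure that reached past the order, self-reported testing, and the SAP leaves it out of its hypotheses, dependent variables and models.

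Timing adds to this. The SAP already reports that nobody screened positive (3.2.2) and gives the stigma scale's reliability in the study sample (4.2). A protocol-listed outcome that disappears without comment from a plan written at that stage invites a question about selective reporting, even if the reason is innocent. What is at stake is whether the trial can say anything direct about its stated secondary aim.

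**Working it through.** **1. Protocol against SAP**

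| Measure | Protocol | SAP |
|---|---|---|
| Kit ordered | Listed analysis, 3.3.11 | Sole uptake outcome, 4.2 and 4.5 |
| Self-reported testing | Listed analysis, 3.3.11 | Absent, no reason given |
| Linkage to care | Listed analysis, 3.3.11 | Absent; moot, as nobody screened positive (3.2.2) |
| Result photo | Collected to confirm uptake, 3.3.5; no listed analysis | Collected, 3.2.2; no analysis |

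The unexplained gap is the second row. The protocol planned for the data: testing history is in the baseline questionnaire (3.3.6) and the follow-up surveys repeat the baseline items (3.3.8). The SAP does not itself confirm that the follow-up item was collected.

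**2. The plan's own figure.** The only power statement (SAP 3.5) is 80% for stigma with 108 per arm and d = 0.39. A noncentral t calculation, two-sided at 0.05, with n multiplied by the Wilcoxon efficiency 3/π, gives 0.796, so it reproduces. It does not bear on uptake, for which no power or rate is given.

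**3. From orders to tests.** In each arm, considering study kits only:

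P(tested) = P(ordered) × P(used given ordered)

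All rates below are assumptions. With orders of 40% (intervention) and 30% (control), a difference of +10 points:

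| Use, intervention / control | Calculation | Difference in tests |
|---|---|---|
| 80% / 80% | 0.40×0.80 − 0.30×0.80 | +8 points |
| 70% / 80% | 0.40×0.70 − 0.30×0.80 | +4 points |
| 60% / 80% | 0.40×0.60 − 0.30×0.80 | 0 |
| 80% / 60% | 0.40×0.80 − 0.30×0.60 | +14 points |

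These are illustrations and do not bound what is possible.

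**4. When the difference vanishes.** It is zero when the use ratio (intervention/control) equals the order ratio (control/intervention): 0.15/0.30 = 0.50, 0.25/0.40 = 0.625, 0.30/0.50 = 0.60.

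**5. A significant order result with no testing difference.** Take 43 versus 27 orders of 108 per arm. The difference is 16/108 = 0.148 and the pooled rate 70/216 = 0.324. The standard error is √(0.324 × 0.676 × 2/108) = 0.0637, so z = 2.33 and p = 0.020. If 50% of intervention and 80% of control orderers use the kit, then 0.40 × 0.50 = 0.25 × 0.80 = 20% test in each arm.

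**6. Equal use.** The direction is kept but power falls. For orders of 40% versus 25% with 108 per arm (unadjusted, two-sided 0.05), power is 0.66 on orders, and on tests 0.59, 0.52 and 0.39 at 90%, 80% and 60% use.

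**The case against.** The strongest reply is that the SAP keeps the protocol's first-listed testing outcome and states its definition openly. That stands. A reader might infer that the SAP switched to an easier endpoint after seeing data; protocol 3.3.11 rules that out, and nothing in the documents shows intent behind the omission.

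A reader might also infer that photo confirmation was removed. It was not: the protocol's analysis section never made it an endpoint, submission was optional, and SAP 3.2.2 still describes it. It is collected and unused, which is no departure from the protocol.

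Next, both arms get the same ordering link (protocol 3.3.5 and 3.3.9) and SAP 3.2 says participants were blinded to arm. No passage suggests that kit use among orderers differs by arm, and with equal use more orders means more tests. This also stands, so a positive result should not be read as false or empty.

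Finally, orders need no follow-up survey. Self-report does, and SAP 4.6 restricts analysis to participants with outcome data and imputes nothing. Photos depend on willingness to disclose. A stigma-reducing intervention could shift both without any change in testing. That is a good reason to keep orders as the main measure, and against allowing a conclusion on testing only when all measures agree in direction: such a rule has no basis in the documents. It does not explain leaving out a comparison that the protocol listed.

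**Conclusion.** The point holds in a limited form. The SAP's uptake result would be a result about kit orders. It would not directly measure testing, and the protocol's self-reported comparison is missing without a reason from a plan written after data collection.

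The size cannot be fixed from the documents, which give no order or use rates. A reader might infer that the testing gain must lie between zero and slightly below the order gain. That follows only from scenarios in which intervention orderers use kits as often as controls or less often; the reverse pattern gives a larger gain. Increased testing is therefore unmeasured, not refuted. This is a secondary outcome in a pilot seeking preliminary estimates, and the primary stigma analysis is unaffected.

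**What to change.** 1. In SAP 4.2, name the outcome *HIV self-test kit ordered*, and word the first secondary hypothesis and its conclusion to match.
2. Restore the protocol's logistic regression of self-reported HIV testing by three months as a secondary outcome, marked as protocol-specified. State the survey item and time window used. If the item was not collected at follow-up, say so and give that as the reason for omission.
3. Report photo-confirmed testing by arm, with all randomised participants in the denominator, as supportive and descriptive only. Classify no photo as not confirmed, and state that it is not proof of non-use.
4. Report follow-up completion and photo return by arm beside these results.

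The cost is wording, one further model and one table, on data that the protocol planned to collect. The downside is that self-report depends on follow-up completion and photo return is voluntary. Both may differ by arm, and photo-confirmed testing will probably be lower than orders.
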